**Return of Results:**

Once the study is completed, we will send subjects a summary of the results and what they mean. Subjects will not receive their own individual results.

**14. CLOSE-OUT PROCEDURES**

At the conclusion of the study, subjects will receive a mailed letter and phone call with a summary of results, which Arm of investigational product they took (Active or Placebo), and the ClinicalTrials.gov study NCT information. The PI's plan to transfer to UC Irvine will also be shared.

Unblinding: The IDS will reveal the randomized groups of subjects to the PI and Coordinators one day after the final subject lab visit. Lab staff will remain blinded until the assay processing is completed. Unblinding is allowed before analysis.

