- Our research coordinator will use eRecord EMR to screen patients for enrollment based on inclusion and exclusion criteria listed above in section #5. Each week, the research coordinator (RC) will screen subjects scheduled to visit to Kidney Clinic within the upcoming 4 weeks for enrollment. The RC will discuss with [name], who will make the final decision for inclusion and exclusion.
- The pre-screening data for potential subjects who choose not to participate or are ineligible will be deleted.

3. Informed consent and buccal swab for *GSTM1* genotyping: Buccal (cheek) swab sample will be obtained from subject: To extract DNA for *GSTM1* genotyping to assess the effect of *GSTM1* genotype on clinical and biochemical response. Genotyping will be performed as previously done. Each study participant will be assigned a subject ID by the RC after obtaining informed consent. The testing supplies for the buccal swab will be labeled by subject ID only and the lab will perform the genotyping.

3. Randomization: Randomization will be performed by the Investigational Drug Service (IDS) who will be provided the patients' CKD stage. The investigators and subjects will be blinded to the randomization of the study supplement and placebo.

At the onset, the IDS will be provided the CKD stage of each study participant (Stage 3 eGFR 30 - < 60 ml/min/1.73 m^2, Stage 4  $\geq$  20 – 29 ml/min/1.73 m^2), The URM Clinical Research Pharmacy and IDS will assist us in the randomization and dispensing process (their efforts are included in the NIH budget). The research team, healthcare providers and participants will be blinded to treatment assignment. Based on our patient mix in our clinic, we expect ~ 60% will be Caucasian, 40% will be AA, and ~ 50% will be female in each group.

While randomization will not be determined by *GSTM1* genotype, we will explore the effect of the genotype on response to treatment. After consent, *GSTM1* genotype will be determined from DNA extracted from buccal swab at a routine clinic visit. *GSTM1* genotype is for research purpose only and will be performed in [name] laboratory using established protocol 

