*The Biomarker lab tests* refer to markers of oxidative stress (plasma hydrogen sulfide (H2S), plasma and urine 8-isoprostane, podocyturia (urine nephrin) to assess glomerular damage, and inflammation (plasma interleukin-6 (IL-6)) will be assessed. Peripheral blood mononuclear cells will be extracted from whole blood and saved for analysis of mRNA levels of cytoprotective enzymes (NQO1, HO-1, AKR1C1, GSTM1), and heat shock proteins (HSP27 and HSP70) . The plasma H2S testing will be performed on coded samples at Cedar-Sinai and there is an MTA for it.

We will perform a urine pregnancy POCT for subjects of child-bearing potential, unless subject reports having had a hysterectomy or if subject is over 50 years of age and the last menstrual cycle was two or more years ago.

Note:

1. If patient gets their labs done before their routine clinic visit, consent will be obtained at the time they come in for their labs (if SMH). If they get their routine SOC labs done at a location that is not SMH i.e. [name] before their routine clinic visit, they will be asked to provide another blood and urine sample (for biomarker lab tests only) at SMH and the research study will pay for them.
2. Patients from non-SMH locations will be asked to travel to SMH as blood samples need to be processed at [name] research lab immediately after blood draw.
3. If the subject decides to have their routine clinic visits and/or SOC lab tests done at a non-SMH location, the study coordinators will collect this data from provider ordered SOC tests from EMR.

For each lab visit related to the study, the study coordinators will carry the requisition that lists the tests to be performed by the URM Central Lab and who would be billed (patient's insurance or research study). For example, if the patient has already had their SOC tests done, the study coordinators will indicate on the requisition that they need labs (blood and urine) for the biomarker lab tests only and it is to be billed to the research study.

On UR Box, the study coordinators will keep track of whether each lab visit was paid for by the patient's health insurance or the research study.

*Questionnaires at baseline visit & each month after:*

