**16. DATA / SAMPLE STORAGE FOR FUTURE USE**

Samples will be collected, processed, and stored for future use in an approved -80°C freezer. To minimize costs, they will be run in batches based on the number of samples that can be loaded on commercially available kits. As this is conducted under an IND, the samples will be stored for 2 years after marketing approval or for 5 years, whichever is later. Only [name] and the investigative team will have access to the

Page 14 of 19

Version 1 Approval Date: 03May2023

Version Date: 05Jan23 TL / 28Jan23 RG / 30Jan23 AJS / 28Feb23 AJS / 06Mar23 SS / 13Apr23 SS/ 02May23 AJS / 08May2023 SS / 28Aug2023 SS / 8July2024 SS / 13Nov2024 AJS

stored data and samples.

The investigative team may elect to share with other researchers and/or utilize subject data and biospecimens collected during this study for future research purposes. This includes subject samples, health information, and genotype GSTM1 data. Subjects will be provided the opportunity to opt-in or opt-out of permitting the study team to utilize their data and biospecimens during the ICF process. Should subjects agree to allow the study team to utilize data and biospecimens for future research, the data and biospecimens would be used to further understand kidney disease and other related topics.

The clinical data and associated biospecimens will be identified only by the Subject ID used in the current study. Computers housing the data are secured in locked rooms when not in use. All data files and derived analytic data files are encrypted for storage and transport. Study data will be kept on password protected computers at URM, REDCap and UR Box program. Signed consent forms will be stored in a cabinet in a locked room.

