## **18. DATA ANALYSIS PLAN – To be performed at UVA**

### Data harmonization, management and analysis

1. Develop data management and statistical analysis plan.
2. Work with the team and CTSI at URMU closely to design a unified management system for data collection, transfer between the study site and management.
3. Data oversight and monitoring during data collection and integration.
4. Harmonize the study data elements and variables from clinical and laboratory and biochemical data
5. Validate data quality and perform cleaning process.
6. Work closely with the PI and clinical investigators to determine appropriate statistical methods and machine learning algorithms for the clinical hypotheses. Cutting-edge statistical methods and innovative data science tools will be considered or adopted.
7. Prepare the analytical datasets and perform pre-stated statistical analyses.
8. Prepare the final results for manuscript writing and submission, conference presentations and publications.

**Power calculation:** The primary outcome of interest in this study is plasma 8-isoprostane, one of the markers of oxidative stress. Based on: 1) the inverse correlation between 8-isoprostane and eGFR (Figure 1 of Cottone *et al.*), 2) the average 8-isoprostane for hypertensive patients of  $262 \pm 137$  pg/ml, 3) a range from 350 to 550 pg/ml for CKD Stages 3-4 patients, and 4) therefore the assumption that the average 8-isoprostane would be  $400 \pm 150$  pg/ml in placebo group, we hypothesize that Avmacol ES would reduce by 25%, approximately at 300 pg/mL.

According to power calculations, the minimum number of participants that need to be recruited is 88. To address the challenges of recruiting patients with stage 4 CKD, there will not be a fixed proportion of patients with CKD stage 3 and 4 that will make up the final 88. However, an equal number of subjects

regardless of CKD stage (44 each) will be assigned by the IDS to the Avmacol ES and placebo arm of the study. **The final 88 will include the ones already enrolled.**

If study participants drop out, additional patients with CKD stage 3 or 4 will be recruited to reach this number. For example, if 8 out of 88 participants drop out, 8 more would be enrolled so the final number of enrollments would be 96.

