**Statistical Analysis:** The data for safety and feasibility assessment will be summarized descriptively with respect to adverse events and compliance with Avmacol ES intake. The difference between the two treatment groups will be evaluated with Chi-square test, and logistic regression if necessary. Distributions of outcome variables will be examined graphically for asymmetry and for outliers. If a lack of symmetry is noted, the variable will be transformed before analysis. The group-specific data will be summarized and reported as mean  $\pm$  SD or median (interquartile range) for continuous measures and as frequency and percentage for categorical measures and their differences will be compared using two-sample *t*-tests or Chi-square test. Those baseline characteristics that are significantly different between the 2 groups will be adjusted in the subsequent analyses. Since plasma 8-isoprostane will be measured at baseline, 1, 3, and 6 months, the effect of Avmacol will be explored at each time point with *t*-test or linear regression to detect an early effect of Avmacol at 1 or 3 months and to determine if such effect will be sustained at 6 months while the patients remain on Avmacol. The effect of Avmacol on longitudinal plasma 8-isoprostane measures will be analyzed with linear mixed effects model, adjusting for potential confounding factors such as age, initial BMI, and baseline characteristics identified in the preliminary analysis. Other factors that might affect the results (such as physical activity and dietary intake) will also be examined. Similar analyses will be performed for the secondary outcomes, including plasma IL-6, urine 8-isoprostane, and urine nephrin. We will also explore the effect of Avmacol on eGFR with linear mixed effects modeling by comparing the slope of eGFR decline between groups, and to the previous 6 months within group, and the effect of *GSTM1* genotype on the response to Avmacol. Additionally, penalized regression and machine learning methods such as random forests algorithm will be considered and applied to fully evaluate the treatment effect and predictability of Avmacol and other important predictors on the outcomes.

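### Section 14 lets the PI and coordinators learn the allocation before the database is locked or the analysis choices are fixed; only assay processing is stated to stay blinded afterwards

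*Combined protocol and SAP*

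**What the plan says.** On blinding during the trial, Section 8 (Randomization) states: "The research team, healthcare providers and participants will be blinded to treatment assignment". It gives no end point for that blind.

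Section 14 (Unblinding) supplies the end point in three sentences. The first sets the timing: "The IDS will reveal the randomized groups of subjects to the PI and Coordinators one day after the final subject lab visit". The second protects the laboratory: "Lab staff will remain blinded until the assay processing is completed". The third is a general permission: "Unblinding is allowed before analysis".

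Section 16 says of the stored samples: "To minimize costs, they will be run in batches based on the number of samples that can be loaded on commercially available kits". For plasma hydrogen sulfide, Section 8 adds that "testing will be performed on coded samples at Cedar-Sinai".

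Section 18 places the analysis at UVA. Item 1 lists developing the data management and analysis plan as a task, item 5 lists validation and cleaning, and item 7 refers to pre-stated analyses. None has a date or a position relative to code release. Item 6 reads: "Work closely with the PI and clinical investigators to determine appropriate statistical methods and machine learning algorithms for the clinical hypotheses". The Statistical Analysis paragraph then leaves choices to inspection of the data, for example: "If a lack of symmetry is noted, the variable will be transformed before analysis".

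**The concern.** A double-blind trial normally keeps the allocation hidden until the data are final and the analysis is fixed. Until then, people can still affect the result by how they resolve a query, classify a late report, treat an extreme value or choose a model. Here the people who receive the codes are the coordinators, who handle adverse-event calls, tablet counts and questionnaires, and the PI, who helps settle the methods. If they know the arms while those matters are open, their decisions can lean one way without anyone intending it. The trial could then not show that data handling and analysis choices were made blind, for either the tolerability aim or the biomarker aim. This rests on an express rule in Section 14, not only on something left unsaid.

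**Working it through.** The plan gives no figure on this point, and the sample size of 88 does not bear on it. The check is therefore a comparison of the sections.

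1. **State of the assays at code release.** Section 8 has plasma, serum and urine frozen at -80°C for later analysis, and Section 16 has them run in batches. Section 14 releases the codes one day after the last lab visit. Its separate protection for lab staff matters only if assays continue after that day, so the plan itself expects some to be outstanding.

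2. **State of the clinical data at code release.** The Schedule of Assessments places the last adverse-event review, questionnaires and tablet review at Month 6, alongside the blood and urine samples. These are therefore due before release. Paper, mailed and emailed questionnaires are allowed (Section 8), and cleaning is a UVA task (Section 18, item 5). No database lock or blinded data review is described. Queries may thus still be open one day after the last visit. Section 15 gives the investigative team access to the ID key, so people who know the arms can link them to subjects.

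3. **State of the analysis choices** (Section 18, Statistical Analysis):

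| Choice | What is given | What is left open |
|---|---|---|
| Transformation | Triggered by visible asymmetry | No criterion and no named transformation |
| Outliers | Graphical inspection | No rule for what is then done |
| Covariates | Age, initial BMI, and baseline variables that differ significantly between arms | Final set; activity and diet are also to be examined |
| Time point | Months 1, 3 and 6 | None named as primary |
| Model | Visit-wise t-test or linear regression; linear mixed model | Which is primary; penalized regression and random forests are also to be considered |
| Analysis set | Drop-outs are replaced | No set defined |

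4. **Who settles them, and when.** Under item 6, UVA does so together with the PI and the clinical investigators. Items 1 and 7 show that a plan and pre-stated analyses are intended. Nothing requires them to be finished before the codes are released.

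5. **Putting these together.** The following order complies fully with the text: last lab visit, codes to the PI and coordinators the next day, remaining queries resolved, methods settled with the PI, analysis. The order last visit, assays, lock, signed plan, codes, analysis is not required anywhere. After the reveal, the only stated blind is that of the lab staff. Section 14 names the PI and coordinators as recipients and is silent on UVA.

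**The case against.** The case on the other side is substantial, and much of it stands.

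- **The core of the double blind is intact.** Codes are released after the final subject's lab visit, so dosing and all scheduled visits are covered. Lab staff stay blinded, so plasma 8-isoprostane and the secondary markers (IL-6, urine 8-isoprostane, urine nephrin) are measured blind. A reader might infer that the double-blind claim fails for every later data-dependent decision. The documents do not support that.
- **Most safety data are planned for collection before release**, and Section 15 describes direct entry into REDCap. A reader might infer that adverse events are attributed after unblinding. No such step is described. What remains is the narrower matter of late entries and queries.
- **The order is permitted, not required.** Section 18 lists the analysis plan first among its tasks, mentions oversight during data collection, and places analysis at a separate institution on de-identified data. UVA may in practice finish the plan early and remain blinded. That would remove much of the concern, but nothing commits them to it.
- **Several choices do not need the identity of the arms.** Asymmetry can be seen in pooled data, and a baseline imbalance can be found with two unnamed groups. This stands. It means that later code release alone would not cure the open choices; a plan fixed in advance is also needed.
- **The size cannot be taken from multiplicity.** A reader might simulate choice among the three visits and call the inflated error rate the cost of unblinding. In 20,000 simulated null trials with 44 per arm and assumed between-visit correlations of 0.3, 0.5 and 0.7, at least one of the three tests reaches p<0.05 in 13.7%, 12.2% and 10.8%. Swapping the arm labels leaves those rates unchanged, because a two-sided p-value does not depend on which arm is called active. One test fixed in advance gives about 5% whenever the codes are released. Those rates measure the lack of a primary time point, not the effect of knowing the arms.
- **This is a pilot seeking preliminary evidence.** That lowers the stakes, but it does not make the permission useful to the trial.

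**Conclusion.** The point holds in a limited form. Section 14 allows the PI and coordinators to know the arms before any stated database lock and before the open choices in Section 18 are fixed, and the PI takes part in those choices. Data queries and analysis choices may therefore be made with knowledge of allocation. The bias is not quantified, and the documents offer no basis for a number.

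The conclusion rests on three things: the absence of a lock or sign-off rule in the text available to this review (part of the text next to the DSMB section was not available); the inference that queries can still be open one day after the last visit; and the unstated blinding status of the UVA analysts. It does not extend to treatment, scheduled visits or assay processing. It deserves action before codes are released, because the protection cannot be restored afterwards.

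**What to change.** In Section 14, delete "Unblinding is allowed before analysis" and state that the IDS releases the allocation to the PI and coordinators only after all of the following:

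1. The primary and secondary assays are complete.
2. Adverse-event, tablet-count and questionnaire data have been entered, queried and locked.
3. An analysis plan has been signed and dated. It should name the primary time point and model, the transformation and outlier rules, the covariates and the analysis set.

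State also that UVA works with dummy arm codes until then. The signed plan matters as much as the later release, since dummy codes alone would not prevent selection among open analyses. Emergency unblinding through the IDS (Section 4.2) and the DSMB's unblinded safety review stay as they are.

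The cost is one revised paragraph in Section 14, completion of the analysis plan already listed in Section 18 by a defined point, and a later reveal to the PI, coordinators and subjects. The length of that delay cannot be stated, because no completion date is given for the batched assays. No extra visits are needed.

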**15. PRIVACY AND CONFIDENTIALITY OF SUBJECTS AND RESEARCH DATA**

The research team consists of URMC clinical providers (Nephrologists) and as such have access to all of the relevant clinic records. Study data will be collected and managed using REDCap electronic data capture tools hosted at URMC. Study data will be directly entered into REDCap, a HIPAA-compliant database. Only de-identified data will be analyzed, and de-identified data will be stored in a password-protected database only available to the research team.

With regard to patient confidentiality, the risk of improper access, use, or disclosure of participant data is minimized through the following procedures:

1. All study personnel and researchers are required to sign a pledge of confidentiality, committing to safeguard the study data during its collection, analysis, and after the study is concluded.
2. Physical (paper) questionnaire forms and media containing the electronic data files will be kept in locked files with restricted access.
3. Data Key- Each subject will be assigned a study ID number which will be used to label their data/samples and linked to the subject on a separate key. Only [name] and the investigative team will have access to the data key and it will be stored separately from the dataset.
4. The data upon which statistical analysis will be conducted will contain participant numbers as unique identifiers in lieu of names, medical record number, or social security numbers. These data are considered identifiable, but not directly identifiable.

When data generated from this study is shared for analysis, only de-identified information will be exchanged. No protected health information will be shared with any collaborator nor used in any publications. Only aggregate results, not individual data, will be published in reports or manuscripts.

**16. DATA / SAMPLE STORAGE FOR FUTURE USE**

Samples will be collected, processed, and stored for future use in an approved -80°C freezer. To minimize costs, they will be run in batches based on the number of samples that can be loaded on commercially available kits. As this is conducted under an IND, the samples will be stored for 2 years after marketing approval or for 5 years, whichever is later. Only [name] and the investigative team will have access to the

Page 14 of 19

Version 1 Approval Date: 03May2023

Version Date: 05Jan23 TL / 28Jan23 RG / 30Jan23 AJS / 28Feb23 AJS / 06Mar23 SS / 13Apr23 SS/ 02May23 AJS / 08May2023 SS / 28Aug2023 SS / 8July2024 SS / 13Nov2024 AJS

stored data and samples.

The investigative team may elect to share with other researchers and/or utilize subject data and biospecimens collected during this study for future research purposes. This includes subject samples, health information, and genotype GSTM1 data. Subjects will be provided the opportunity to opt-in or opt-out of permitting the study team to utilize their data and biospecimens during the ICF process. Should subjects agree to allow the study team to utilize data and biospecimens for future research, the data and biospecimens would be used to further understand kidney disease and other related topics.

The clinical data and associated biospecimens will be identified only by the Subject ID used in the current study. Computers housing the data are secured in locked rooms when not in use. All data files and derived analytic data files are encrypted for storage and transport. Study data will be kept on password protected computers at URM, REDCap and UR Box program. Signed consent forms will be stored in a cabinet in a locked room.

